11.3 Exploratory endpoint

- 11.3.1 The feasibility of capturing patient reported outcomes (FACT-Br) electronically in the Radiation Oncology clinic will be assessed. Feasibility will be defined as 75% or greater compliance with electronic completion of the questionnaire at the specified time points.

11.4 Toxicity evaluation

- 11.4.1 Acute and late toxicity will be graded per the CTCAE version 4.0.
- 11.4.2 Definition of acute toxicity: any possible, probable, or definite treatment-related AE or SAE occurring within 90 days of the completion of radiotherapy.
- 11.4.3 Definition of late toxicity: any possible, probable, or definite treatment-related AE or SAE occurring later than 90 days from the completion of radiotherapy.

11.5 Dose Escalation and statistical considerations

11.5.1 The modified toxicity probability interval (mTPI) method with adjustment based on observed dose limiting toxicity (DLT) rate will be employed in decision making concerning dose escalation within each cohort investigated.³⁵ The assumptions to be applied in establishing the mTPI methodology are:

- Each specific tumor size cohort exploration may include up to 30 patients for a total enrollment of up to 60 patients.
- The MTD is defined to have 0.20 probability of toxicity.
- The acceptable variance around the MTD is ± 0.05 (i.e., the region of the MTD is 15% to 25% incidence of dose limiting toxicity).

The dose assignment recommendations for cumulative number of patients are presented in Table 11.1. The size of each patient cohort during the dose escalation phase of the study will be at least 3 patients. Once the initial three evaluable patients have cleared the DLT evaluation period then an mTPI design will be used to determine whether to escalate or de-escalate the dose. Up to 10 evaluable patients may be enrolled at a specific dose prior to making a final dose escalation/de-escalation decision. If the DLT rate of the current dose does not exceed the maximum permitted toxicity rate as defined by the mTPI, then we will evaluate the next dose level. Patients not evaluable for assessment of DLT may be replaced. For any subsequent cohort of patients, the recommended dose assignment action will be based on the total number of patients with DLTs in the current and prior cohorts treated at the same dose level. For example, if a cohort of 3 patients are treated at dose level 1 for the first time and one of them experiences a DLT, then the recommended action for the next cohort of patients will be to stay at the current dose level (S); if this recommendation is accepted, then the selected dose level for the next cohort of patients will be 1; if a total of 6 additional patients are treated at dose level 1 and there are no more DLTs observed, then the cumulative number of patients treated at dose level 1 is 9, and the cumulative number of patients with DLTs at dose level 1 is 1 out of 9, thus the recommendation would be to escalate the dose for the subsequent cohort (E).

The dose escalation plan will allow enrollment of a three-patient cohort prior to the mTPI rule taking effect at the beginning of each dose level. Up to three patients can be enrolled at the beginning of each dose escalation level. Those three patients must be followed throughout the dose evaluation period (90 days). If one of those three patients develop a DLT, then cohorts of up to three additional patients may be treated at that dose level and be within the 90-day evaluation period at any given time. For example, if 1 out of the 3 patients develops a DLT, then patients 4-6 may then be enrolled. Patient 7

may be enrolled after patient 4 has been followed without toxicity for 90 days.

Dose-finding for a cohort may be stopped when one of the following criteria is met:

- The lowest dose level appears too toxic after at least 3 patients are dosed at that dose level.
- The maximum sample size in dose finding of 30 evaluable patients per cohort has been reached.
- A minimum of 10 evaluable patients have been treated at the estimated MTD.

Analysis will be descriptive and exploratory. Data will be summarized and listed by dose level. Toxicity, local tumor control local, central nervous system disease control in accordance with the Response Assessment in Neuro-Oncology (RANO) criteria for brain metastases, and QOL, will be presented in the form of patient data listings that include, but are not limited to, age, gender, dose, and tumor response at each visit. If the data permits, local tumor control rate, central nervous system disease control rate and corresponding exact confidence interval will be calculated. Additional exploratory data analysis will be performed as data permits.

Interim review of enrolled patients demonstrated that the first three patients were not evaluable at the timepoint for the primary endpoint due to systemic disease progression and/or other medical illnesses that were deemed to be unrelated to their radiation treatment. This was presented to the clinical trials monitoring committee, and it was decided that study continuation was appropriate; however, it was agreed upon that there should be enrollment of 6 patients at dose level 1 in the cohort of patients with tumors 2.1–4 cm in diameter prior to consideration of dose escalation in order to ensure safety. After this, dosing decisions will return to the originally proposed chart as displayed below.

Table 11.1 Dose Escalation rule of the modified toxicity probability interval method

	3	4	5	6	7	8	9	10	11	12	13	14	15	16	17	18	19	20	21	22	23	24	25	26	27	28	29	30
0	E	E	E	E	E	E	E	E	E	E	E	E	E	E	E	E	E	E	E	E	E	E	E	E	E	E		
1	S	S	S	S	S	S	E	E	E	E	E	E	E	E	E	E	E	E	E	E	E	E	E	E	E	E		
2	DU	D	S	S	S	S	S	S	S	S	S	S	S	E	E	E	E	E	E	E	E	E	E	E	E	E		
3	DU	DU	DU	DU	D	S	S	S	S	S	S	S	S	S	S	S	S	S	S	E	E	E	E	E	E	E		
4	DU	DU	DU	DU	DU	D	S	S	S	S	S	S	S	S	S	S	S	S	S	S	S	S	S	S	S	S		
5	DU	S	S	S	S	S	S	S	S	S	S	S	S	S	S	S	S											
6	DU	DU	S	S	S	S	S	S	S	S	S	S	S	S	S	S	S											
7	DU	DU	DU	S	S	S	S	S	S	S	S	S	S	S	S	S	S											
8	DU	DU	DU	DU	S	S	S	S	S	S	S	S	S	S	S	S	S											
9	DU	DU	DU	DU	DU	S	S	S	S	S	S	S	S	S	S	S	S											
10		DU	DU	DU	DU	DU	DU	S	S	S	S	S	S	S	S	S	S	S										
11		DU	DU	DU	DU	DU	DU	S	S	S	S	S	S	S	S	S	S	S										
12		DU	DU	DU	DU	DU	DU	S	S	S	S	S	S	S	S	S	S	S										
13		DU	DU	DU	DU	DU	DU	S	S	S	S	S	S	S	S	S	S	S										
14		DU	DU	DU	DU	DU	DU	S	S	S	S	S	S	S	S	S	S	S										
15		DU	DU	DU	DU	DU	DU	S	S	S	S	S	S	S	S	S	S	S										
16		DU	DU	DU	DU	DU	DU	S	S	S	S	S	S	S	S	S	S	S										
17		DU	DU	DU	DU	DU	DU	S	S	S	S	S	S	S	S	S	S	S										
18		DU	DU	DU	DU	DU	DU	S	S	S	S	S	S	S	S	S	S	S										
19			DU	DU	DU	DU	DU	DU	S	S	S	S	S	S	S	S	S	S	S									
20				DU	DU	DU	DU	DU	DU	DU	DU	DU	DU	DU	S	S	S	S	S	S	S	S	S	S	S			
21					DU	DU	DU	DU	DU	DU	DU	DU	DU	DU	S	S	S	S	S	S	S	S	S	S	S			
22						E	E	E	E	E	E	E	E	E	S	S	S	S	S	S	S	S	S	S	S			
23							S	S	S	S	S	S	S	S	S	S	S	S	S	S	S	S	S	S	S			
24							D	D	D	D	D	D	D	D	D	D	D	D	D	D	D	D	D	D	D			
25								U	U	U	U	U	U	U	U	U	U	U	U	U	U	U	U	U	U			
26									MTD																			
27																												
28																												
29																												
30																												

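### Does the six-patient hold at dose level 1 fail because it counts enrolled rather than evaluable patients?

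*Combined protocol and SAP*

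**What the plan says.** Section 11.5.1 normally allows a first mTPI decision "Once the initial three evaluable patients have cleared the DLT evaluation period". It adds that "Up to 10 evaluable patients may be enrolled at a specific dose" before a final decision there, and that "Patients not evaluable for assessment of DLT may be replaced". On accrual within a level it says: "If one of those three patients develop a DLT, then cohorts of up to three additional patients may be treated at that dose level".

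The interim-review paragraph of the same section reports that "the first three patients were not evaluable at the timepoint for the primary endpoint", for reasons judged unrelated to radiation. The monitoring committee let the study continue but agreed that "there should be enrollment of 6 patients at dose level 1 in the cohort of patients with tumors" of 2.1–4 cm, "prior to consideration of dose escalation in order to ensure safety". The paragraph closes: "After this, dosing decisions will return to the originally proposed chart as displayed below".

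On size, the 11.5.1 assumptions and the Sample size section (11.6) give at most 30 patients per size cohort and 60 enrolled in total. The stopping criteria in 11.5.1 put the 30 in evaluable patients.

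**The concern.** The hold was adopted because patients could not be evaluated, yet it is worded in enrolled patients. It does not say whether the six must be evaluable or whether the first three are among them. If they are, six enrolled less three non-evaluable leaves three evaluable. Table 11.1 allows escalation at 0/3, so the hold would add no DLT information to the ordinary rule. The accrual text does not settle this, because it describes patients 4–6 only for the case of a DLT among the first three. Replacement is permitted but not required.

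At stake is the first escalation decision in one cohort, which two readers could take on three or on six evaluable patients.

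A smaller question is the cap. If replaced patients count towards 30 and 60, those limits and the limit of 30 evaluable per cohort cannot both be reached.

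**Working it through.** **Inputs.** From 11.5.1: target DLT rate 0.20, acceptable interval 0.15–0.25, first decision at three evaluable patients, up to 10 evaluable per dose. From Table 11.1: the rows for 0 and 1 DLT. Assumed, because the plan does not give them: a uniform Beta(1,1) prior and exclusion of a dose when P(rate > 0.20) exceeds 0.95.

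**Reproducing the plan's decisions.** With these inputs the mTPI rule gives 0/3 E, 1/3 S, 0/6 E, 1/6 S, 1/8 S and 1/9 E. All agree with Table 11.1, and 1/3 and 1/9 agree with the worked example in 11.5.1. At n = 3 and at n = 6, escalation therefore needs zero DLTs.

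**First decision.** With true DLT rate p and q = 1 − p, the chance of E is q³ with three evaluable patients and q⁶ with six.

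| p | q³ | q⁶ |
|---|---|---|
| 0.20 | 0.512 | 0.262 |
| 0.30 | 0.343 | 0.118 |
| 0.40 | 0.216 | 0.047 |

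**By nine evaluable patients, adding groups of three.** Starting with three, E is reached at 0/3, or at 1/9 after one DLT in the first three: q³ + 3p·q²·q⁶ = q³ + 3p·q⁸. Starting with six, E is reached at 0/6, or at 1/9 after one DLT in the first six: q⁶ + 6p·q⁵·q³ = q⁶ + 6p·q⁸.

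| p | Start with three | Start with six | Difference |
|---|---|---|---|
| 0.20 | 0.512 + 0.101 = 0.613 | 0.262 + 0.201 = 0.463 | 0.149 |
| 0.30 | 0.343 + 0.052 = 0.395 | 0.118 + 0.104 = 0.221 | 0.173 |
| 0.40 | 0.216 + 0.020 = 0.236 | 0.047 + 0.040 = 0.087 | 0.149 |

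Differences are taken before rounding.

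**Precision with no DLT.** The exact one-sided 95% upper bound on the rate is 1 − 0.05^(1/3) = 0.632 after 0/3 and 1 − 0.05^(1/6) = 0.393 after 0/6.

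**What the weak reading requires.**

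1. All three non-evaluable patients were in the 2.1–4 cm cohort at dose level 1. The paragraph says only that they were the first three, and gives neither cohort nor dose level. Placing the hold at that level implies it, but does not state it. If one of them was in the 4.1–6 cm cohort, six enrolled at this level less two non-evaluable leaves four evaluable, and the three-versus-six comparison no longer applies.
2. Those three count towards the six. The text is silent. The sentence sets the hold against simple continuation, gives safety as its purpose and then returns to the chart. A return implies a departure, and the chart already allows escalation at 0/3. If the hold could be met with three evaluable patients, those words would do almost nothing.

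**The floor under either reading.** The requirement that three evaluable patients clear the DLT period is untouched. It is the rule at every other dose level and in the other cohort.

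**Cap.** If replaced patients count, 60 enrolled leaves at most 60 − 3 = 57 evaluable, and 30 evaluable in each cohort needs at least 60 + 3 = 63 enrolled. Three levels × 10 evaluable per dose = 30, so the stopping limit matches the design's own maximum. Ten assumed three-level DLT profiles (rates 0.05–0.40) were simulated with 20,000 runs each, groups of three, and stopping at 10 on the current dose or when level 1 is too toxic. The mean need was 10.4–16.8 evaluable per cohort with a first group of three and 10.5–19.5 with a first group of six. More than 27 were needed in 0.46–1.70% and 0.64–3.30% of runs. No run needed more than 30.

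**The case for a change.** The strongest case for a change is that an escalation safeguard should not rest on inference. The plan separates enrolled from evaluable patients elsewhere in the same section, then drops the distinction in the one measure prompted by non-evaluability. If the committee meant six evaluable patients, the protocol does not strictly require what was agreed. Later looks do not remove the gap: it is still 15–17 percentage points by nine patients.

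Much of this stands. The ambiguity is real, the arithmetic is right, and one added word would remove it. But the gap measures how much an extra safeguard adds to the base design. It does not show that the base design is wrong. The effect on the final choice is also smaller than at the first look. In a simulation with the stopping assumptions above and an assumed isotonic selection rule, true rates of 20/30/40% led to a level above 1 being chosen in about 34% of runs with a first group of three and about 24% with six. With true rates of 5/10/20%, level 3 was chosen in about 64% and 63%.

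The accrual text adds little to the objection. It is not the only route to more patients, since 11.5.1 also allows up to 10 evaluable at a dose and replacement of the non-evaluable. The hold is the specific provision for this level.

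**Conclusion.** No change to the plan follows. The hold sentence leaves out a detail, but no stated rule gives a wrong result. The weak reading depends on two unstated premises and goes against the sentence's own purpose, and even then it falls back to the minimum that applies everywhere else in the design. Rewording would only record what the committee agreed, and the trial team can read that from the committee's record. This review does not say which count is right.

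The size, if the readings did diverge, is 51% versus 26% for escalation at the first decision at a true DLT rate of 20%, and 61% versus 46% by nine patients. It is confined to one dose level of one cohort, with Table 11.1, the target and the DLT definition unchanged. These figures use decision cells that match Table 11.1, and treat patients as independent with a common DLT rate.

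The cap is an editorial matter. Both figures are upper limits, nothing requires both to be reached, the analysis is descriptive, and under the assumed profiles more than 27 evaluable patients per cohort were needed in at most about 3% of runs.

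### Does the six-patient step at dose level 1 of the 2.1-4 cm cohort suspend the mTPI chart's de-escalation signals until six patients are enrolled?

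*Combined protocol and SAP*

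**What the plan says.** The general rule in Section 11.5.1 is "Once the initial three evaluable patients have cleared the DLT evaluation period then an mTPI design will be used", and its purpose is "to determine whether to escalate or de-escalate the dose". The same section lets as many as ten evaluable patients be treated at one dose before the decision on it is final. It allows non-evaluable patients to be replaced, and it describes the chart's output as a recommendation that may or may not be accepted. Places 4 to 6 at a level are described as opening when one of the first three patients has a DLT.

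Among the criteria introduced by "Dose-finding for a cohort may be stopped when one of the following criteria is met" is this one: "The lowest dose level appears too toxic after at least 3 patients are dosed at that dose level".

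The interim-review paragraph then reports that "the first three patients were not evaluable at the timepoint for the primary endpoint". After the clinical trials monitoring committee had considered this, "it was agreed upon that there should be enrollment of 6 patients at dose level 1" of the 2.1-4 cm cohort, "prior to consideration of dose escalation in order to ensure safety". It closes with "After this, dosing decisions will return to the originally proposed chart as displayed below".

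In Table 11.1, two DLTs read DU at n = 3, D at n = 4, and S at n = 5 and n = 6. Three DLTs in six read DU. Level 1 is the lowest level in the dose schedule (Table 2.2 and Section 6.7).

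**The concern.** The two starting points differ in number (three or six), in unit (evaluable with the DLT period completed, or enrolled) and apparently in scope. The closing sentence speaks of dosing decisions in general, and a return to the chart suggests that the chart was set aside in the meantime. On that reading, two DLTs in the first three evaluable patients would not trigger the chart's DU. Accrual would go on to six, and the same two DLTs would then read S. A step added for safety would be less protective than the rule it modifies, with up to three more patients treated at level 1.

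Two further points add to the impression. The step was adopted because three patients were not evaluable, yet it counts enrolled patients and does not say whether those three are among the six. The accrual text also gives no explicit route to places 4 to 6 when none of the first three has a DLT.

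**Working it through.** **1. Reproduce the chart cells.** Section 11.5.1 gives a target of 0.20 and an acceptable region of 0.15 to 0.25. It gives neither the prior nor the unacceptability cut-off, so a uniform prior and 0.95 are assumed. With x DLTs in n patients the posterior is Beta(1+x, 1+n-x). Each interval's posterior probability is divided by its length, and the largest value gives E, S or D. If P(rate > 0.20) exceeds 0.95, the cell is DU.

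| x/n | E | S | D | P(rate > 0.20) | Decision |
|---|---|---|---|---|---|
| 2/3 | 0.080 | 0.388 | 1.266 | 0.973 | DU |
| 2/6 | 0.492 | 1.698 | 1.009 | 0.852 | S |
| 3/6 | 0.081 | 0.585 | 1.239 | 0.967 | DU |

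These match Table 11.1, as do the rows for 0 to 3 DLTs at every n from 3 to 10. The section's worked example also reproduces (1/3 is S, 1/9 is E).

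**2. How often could the literal reading matter?** Let p be the true DLT rate at level 1 (assumed) and q = 1 - p.

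- First look at which the chart reads DU (2 or 3 DLTs in 3): 3p²q + p³.
- DU at three becoming S at six. This needs 2/3 and then 0/3, because three or more DLTs in six still read DU: 3p²q × q³ = 3p²q⁴.

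| p | 2 or 3 DLTs in 3 | 2/3, then 2/6 |
|---|---|---|
| 0.15 | 6.1% | 3.5% |
| 0.20 | 10.4% | 4.9% |
| 0.25 | 15.6% | 5.9% |
| 0.30 | 21.6% | 6.5% |
| 0.40 | 35.2% | 6.2% |

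For example, at p = 0.20: 3 × 0.04 × 0.4096 = 0.049. At 15% to 25% the level lies inside the protocol's own MTD region, so an S there is not a wrong answer.

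**3. Counting unit.** With six evaluable patients, the chart first recommends escalation only at 0/6 (1/6 reads S), which has chance q⁶. If three of the six give no DLT information, the chance is q³.

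| p | q³ | q⁶ |
|---|---|---|
| 0.15 | 61% | 38% |
| 0.25 | 42% | 18% |
| 0.30 | 34% | 12% |

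The q³ column is what the ordinary three-evaluable rule gives. The looser count would forfeit the extra caution but would not fall below the general plan. It also removes the de-escalation worry: with only three evaluable patients the chart is read at n = 3, where two DLTs are DU.

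**4. The passages side by side.** The six-patient condition is attached to escalation. The closing sentence refers back to that condition, and no sentence says that de-escalation waits. At level 1 a D or DU has no lower level to move to, so the available response is to stop. The criterion for that applies from three patients and is not altered by the interim paragraph.

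**The case for a change.** The strongest case for a change is that an exception should state its scope and its unit, and this one states neither. No sentence says de-escalation waits for six, and none says it stays at three. The stop at the lowest level is permissive. The accrual text gives no route to six after 0/3, which is a common result (q³ is 61%, 51% and 42% at rates of 15%, 20% and 25%). If the first three non-evaluable patients count, the step adds nothing.

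Part of this stands: the paragraph is loosely worded, and its unit and the status of the first three patients are left open. The rest carries less weight.

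- The permissive wording applies to both sides, since the chart's outputs are recommendations too. The general rule also already allows a final decision, in either direction, after more than three patients.
- A strict reading of the accrual sentence cannot be used selectively. If places 4 to 6 open only after exactly one DLT, they do not open after two or three DLTs either, and the feared path disappears.
- After 0/3, the committee's specific requirement of six, within the ten allowed per dose, supplies the route. Its only effect there is to delay escalation.
- Counting the first three patients would defeat the stated reason for the step. The section ties chart decisions to evaluable patients who have completed the DLT period, and it allows replacement.

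**Conclusion.** Three and six do not contradict each other. The first is the general start. The second is an exception for one level of one cohort, with its trigger, the body that agreed it and its end point all stated. What remains is missing detail on scope and unit, which a team running the trial can fill sensibly from the rest of Section 11.5.1, so no change to the plan follows.

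If the literal reading were nevertheless followed, the one path that turns a DU into an S has a chance of 3.5% to 6.5% at true DLT rates of 15% to 40%. That figure assumes six evaluable patients, independent outcomes and a common DLT rate; the reproduced cells also assume the uniform prior and 0.95 cut-off. This assessment concerns how the passages fit together and takes no position on what the clinical dosing or stopping rule should be.

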11.5 Toxicity rates

11.6.1 The primary endpoint of the study is to assess the rate of dose limiting toxicity experienced within 90 days of the completion of treatment. The maximum tolerated dose is defined to have a dose limiting toxicity rate of 20% or less. This will be assessed according to the mTPI method as described above.

11.6 Sample size

11.6.1 The total number of subjects enrolled in the study may vary as the study may terminate if the DLT rate exceeds the maximum permitted toxicity rate per the mTPI. Each specific tumor size cohort exploration may include up to 30 patients for a total enrollment of up to 60 patients.

Appendix A: Karnofsky Performance Status (KPS)

100	Normal. No complaints; No evidence of disease
90	Able to carry on normal activity; minor signs or symptoms of disease
80	Normal activity with effort; some signs or symptoms of disease
70	Cares for self; unable to carry on normal activity or do active work
60	Requires occasional assistance, but is able to care for most personal needs
50	Requires considerable assistance and frequent medical care
40	Disabled; requires special care and assistance
30	Severely disabled; hospital admission is indicated although death is not imminent
20	Very sick; hospital admission necessary, active supportive treatment necessary
10	Moribund; fatal processes progressing rapidly
0	Dead

Appendix B: Response Assessment in Neuro-Oncology Brain Metastases (RANO-BM)

	Complete response	Partial response	Stable disease	Progressive disease
Target lesions	None	≥30% decrease in sum longest distance relative to baseline	<30% decrease relative to baseline but <20% increase in sum longest distance relative to nadir	≥20% increase in sum longest distance relative to nadir*
Non-target lesions	None	Stable or improved	Stable or improved	Unequivocal progressive disease*
New lesion(s)†	None	None	None	Present*
Corticosteroids	None	Stable or decreased	Stable or decreased	Not applicable‡
Clinical status	Stable or improved	Stable or improved	Stable or improved	Worse*
Requirement for response	All	All	All	Any‡

*Progression occurs when this criterion is met. †A new lesion is one that is not present on prior scans and is visible in at least two projections. If a new lesion is equivocal, for example because of its small size, continued therapy can be considered, and follow-up assessment will clarify if the new lesion is new disease. If repeat scans confirm there is definitely a new lesion, progression should be declared using the date of the initial scan showing the new lesion. For immunotherapy-based approaches, new lesions alone do not define progression. ‡Increase in corticosteroids alone will not be taken into account in determining progression in the absence of persistent clinical deterioration.

FACT-BR (Version 4)

Below is a list of statements that other people with your illness have said are important. By circling one (1) number per line, please indicate how true each statement has been for you during the past 7 days.

PHYSICAL WELL-BEING		Not at all	A little bit	Some- what	Quite a bit	Very much
GP1	I have a lack of energy.....	0	1	2	3	4
GP2	I have nausea.....	0	1	2	3	4
GP3	Because of my physical condition, I have trouble meeting the needs of my family.....	0	1	2	3	4
GP4	I have pain.....	0	1	2	3	4
GP5	I am bothered by side effects of treatment.....	0	1	2	3	4
GP6	I feel ill.....	0	1	2	3	4
GP7	I am forced to spend time in bed	0	1	2	3	4
SOCIAL/FAMILY WELL-BEING		Not at all	A little bit	Some- what	Quite a bit	Very much
GS1	I feel close to my friends	0	1	2	3	4
GS2	I get emotional support from my family.....	0	1	2	3	4
GS3	I get support from my friends	0	1	2	3	4
GS4	My family has accepted my illness.....	0	1	2	3	4
GS5	I am satisfied with family communication about my illness	0	1	2	3	4
GS6	I feel close to my partner (or the person who is my main support).....	0	1	2	3	4
Q1	Regardless of your current level of sexual activity, please answer the following question. If you prefer not to answer it, please check this box  and go to the next section.					
GS7	I am satisfied with my sex life.....	0	1	2	3	4

By circling one (1) number per line, please indicate how true each statement has been for you during the past 7 days.

EMOTIONAL WELL-BEING		Not at all	A little bit	Some- what	Quite a bit	Very much
GE1	I feel sad.....	0	1	2	3	4
GE2	I am satisfied with how I am coping with my illness	0	1	2	3	4
GE3	I am losing hope in the fight against my illness	0	1	2	3	4
GE4	I feel nervous	0	1	2	3	4
GE5	I worry about dying	0	1	2	3	4
GE6	I worry that my condition will get worse.....	0	1	2	3	4

FUNCTIONAL WELL-BEING		Not at all	A little bit	Some- what	Quite a bit	Very much
GF1	I am able to work (include work at home).....	0	1	2	3	4
GF2	My work (include work at home) is fulfilling	0	1	2	3	4
GF3	I am able to enjoy life	0	1	2	3	4
GF4	I have accepted my illness	0	1	2	3	4
GF5	I am sleeping well.....	0	1	2	3	4
GF6	I am enjoying the things I usually do for fun.....	0	1	2	3	4
GF7	I am content with the quality of my life right now	0	1	2	3	4

By circling one (1) number per line, please indicate how true each statement has been for you during the past 7 days.

ADDITIONAL CONCERNS		Not at all	A little bit	Some-what	Quite a bit	Very much
Br1	I am able to concentrate.....	0	1	2	3	4
Br2	I have had seizures (convulsions).....	0	1	2	3	4
Br3	I can remember new things.....	0	1	2	3	4
Br4	I get frustrated that I cannot do things I used to	0	1	2	3	4
Br5	I am afraid of having a seizure (convulsion)	0	1	2	3	4
Br6	I have trouble with my eyesight.....	0	1	2	3	4
Br7	I feel independent	0	1	2	3	4
NTX 6	I have trouble hearing.....	0	1	2	3	4
Br8	I am able to find the right word(s) to say what I mean.....	0	1	2	3	4
Br9	I have difficulty expressing my thoughts.....	0	1	2	3	4
Br10	I am bothered by the change in my personality.....	0	1	2	3	4
Br11	I am able to make decisions and take responsibility.....	0	1	2	3	4
Br12	I am bothered by the drop in my contribution to the family.....	0	1	2	3	4
Br13	I am able to put my thoughts together	0	1	2	3	4
Br14	I need help in caring for myself (bathing, dressing, eating, etc.).....	0	1	2	3	4
Br15	I am able to put my thoughts into action	0	1	2	3	4
Br16	I am able to read like I used to.....	0	1	2	3	4
Br17	I am able to write like I used to	0	1	2	3	4
Br18	I am able to drive a vehicle (my car, truck, etc.)	0	1	2	3	4
Br19	I have trouble feeling sensations in my arms, hands, or legs.....	0	1	2	3	4
Br20	I have weakness in my arms or legs	0	1	2	3	4
Br21	I have trouble with coordination.....	0	1	2	3	4
An 10	I get headaches.....	0	1	2	3	4
